6.4. Methodology

6.4.1. Phase 1, CTA Knowledge elicitation

The interview will use a four "sweep" method (see figure 2). Initially, the interviewee will be invited to suggest an appropriate example of where they have had to make a complex decision regarding the personalisation of an ACT regimen for a child or young person with

PCD. This will form the basis of the rest of the interview, with the aim of eliciting information on how the clinician made this decision. The interviewee will be invited to provide an overview of the chosen example, which will be used in the subsequent sweeps to drill down into further detail.

The second sweep aims to provide a more detailed account of the chosen example, adding timelines, and identifying critical points within that timeline where the situation could have changed depending on the decision made at that time. If needed, during this second sweep, the interviewer will clarify points within the timeline so that this is a correct and detailed account ready for the next sweep.

The third sweep explores deeper into the chosen example, in terms of the interviewee's perceptions, expectations, goals, judgments and uncertainties about the example throughout the process, particularly at the critical points identified in the second sweep. The interviewee will be asked about the options they considered when making decisions, what information was needed in order to make this decision.

The final sweep asks questions such as "what if". This is an opportunity to take each point already discussed, and allow the interviewee to consider what they might have done differently, and if they had, what would have happened³².

[figure not shown]

Figure 2: The Critical Decision Method procedure

Interviews will be recorded using an encrypted dictaphone, and clinician participants will be assigned a unique ID number, so that they are not identified by name on the recording.

They will be made aware before beginning that it may be possible to identify them from some of the information that they give as part of the interview, but that data will be reported anonymously, and no identifiable information will be reported.

Interview schedule summary:

Sweep	Prompts
Introduction	Experience, professional training
1.Identify	Overview case
example	Decision to be made
2.Add	Key decision shifts
details/context	Cues What would newly qualified versus experienced physio notice?
3.Progressive	Expectations Reminded of previous case?
deepening	Goals Specifics and priorities
	Judgements Alternatives considered
	Uncertainties How right decision known?
4.What if	Differences and associated outcome If X changed what would
queries	outcome be?
	Anticipated novice errors.

A semi-structured interview script, or topic guide will be further developed and piloted with the help of [name] and paediatric respiratory physiotherapist [name].

Demographic information will be collected for all participants and will include the following:

- Number of years of experience in respiratory care
- Number of PCD patients routinely under their care
- If they have a declared subspecialty interest in PCD

Interviews will be transcribed by the lead researcher, and will be imported into NVivo for processing and identification of themes. Transcripts will be coded and thematic analysis will be conducted. No identifiable information will be included in the transcripts, and participants will be identified on recordings by their study ID number only. Both transcripts and recordings will be stored in a locked cabinet, with recordings transferred to a password-protected, secure area of the University of Sheffield network drive. Transcripts will be anonymised and, in published material, vignettes that avoid speech mannerisms and context (through which participants may be identified) will be avoided. All transcripts and recordings will be stored securely by the researchers at the University of Sheffield for at least 5 years after publication.

The final output of the thematic analysis will be a concept map which will link, goals, cues, expectancies and actions.

6.4.2. Phase 2, Quantitative data collection – effects of intervention on lung function

All patient participants (from LTHT, BTH and SCH) will attend the MRI unit at the University of Sheffield (UoS).

All participants will have assessment by MRI at: baseline, 1-hour and 5-hours post baseline to measure the effects of ACTs immediately post ACT and at 4-hours post ACT based on the anecdotal recommended minimal interval between ACT regimens. Participants in the ACT group will complete their usual ACT regimen immediately after the baseline MRI scan. Those in the non-ACT group will be asked to not intentionally undertake any ACTs between the first and last MRI.

We will ask the referring clinician of all patient participants to provide clinical details from their history including details of their PCD diagnosis and recent health including lung function. Baseline spirometry and PCD-QOL will be performed at the study visit for to assist with defining the study population. As spirometry may cause inadvertent airway clearance it will be performed before the first MRI.

ACT group (n=37):

At the visit the following order of assessments will be used:

- 1. Height and weight
- 2. Baseline spirometry (lung function)
- 3. Oxygen saturations using an infrared light on a clip on their finger for approximately 30-60 seconds.
- 4. MRI-baseline (time 0 hours)
- 5. Physiotherapy ACT review and ACT completion
- 6. MRI- at 1 hour
- 7. QOL-PCD
- 8. MRI- at 5 hours

Non-ACT group (n=6):

At the visit the following order of assessments will be used:

- 1. Height and weight
- 2. Baseline spirometry (lung function)
- 3. Oxygen saturations using an infrared light on a clip on their finger for approximately 30-60 seconds.
- 4. MRI- baseline (time 0 hours)
- 5. MRI- at 1 hour
- 6. QOL-PCD
- 7. MRI- at 5 hours

Each MRI session will comprise of; 10-minute ¹²⁹Xe scan, 2-minute break, 20-minute ¹H scan. Participants will be free to move around between scan-sessions but will be asked to wear a simple pedometer to capture any unusual physical activity between scans. A parent/guardian can come into the scanning room. The POLARIS team are experienced, having completed over 150 exams in children with CF with no adverse events, however the test will be terminated immediately if there is any subject distress.

Summary of imaging methods and quantitative metrics

The MRI scanning will take place on a whole body 1.5T MRI scanner equipped with transmit receive coils for ¹²⁹Xe Hyperpolarised gas MRI. The hyperpolarised gases will be

manufactured under regulatory licence and administered via inhalation from a Tedlar plastic bag. The following images will be taken at each time point:

- ¹²⁹Xe HP breath-hold ventilation imaging of the lung performed at end inspiratory volume and at TLC using 3D steady state free precession sequences³⁷ with coregistered ¹H anatomical imaging³⁸.
- Structural proton ¹H MRI of the lung using a 3D gradient echo sequence acquired at two lung inflation levels FRC and TLC³⁶
- Free breathing ¹H MRI using 75 seconds of free-breathing analysed using the PREFUL technique³⁹ including registration, low-pass filtering, and calculation of fractional ventilation.

The quantitative outcomes will include:

- From HP MRI:
 - Lung ventilated volume (¹²⁹Xe %VV)
 - The co-efficient of variance of ventilated image signal intensity (¹²⁹Xe CVmean).
- From free-breathing ¹H MRI:
 - Lung Ventilated volume (¹H %VV)
 - The co-efficient of variance of ventilated image signal intensity (¹H CVmean).

Airway clearance review

The participant will be asked to complete their usual airway clearance regime with the support of their parent or guardian. This may include taking a saline nebuliser, breathing techniques, the use of positive expiratory pressure device and coughing. The participant will be familiar with this routine as they will have been advised to complete it every day at home. - structure and content to be based on findings from phase 1 but anticipated to include; asking the participant questions about how they feel their ACT is working for them and auscultation palpation of chest wall. This assessment will be video recorded for phase 3.

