6.2.3. Allocation to group (phase 2)

We will allocate patient participants to groups to similarly distribute confounding factors including: age, gender and disease severity indicated by number of exacerbations requiring antibiotics in the last 12 months. A self-audit process will be used during recruitment and allocation to provide regulation to the process and allow adaptations as needed. Accurate reporting will be used to capture any necessary amendments.

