7.5. Subject withdrawal, breaking the blind and trial stopping/discontinuation rules

This is not a blinded study. Subjects can withdraw from the study at any point. This will not affect their clinical care. An attempt to find a replacement subject will be made if the study remains within the recruitment window.

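### QOL-PCD is meant to help define the study population, but it is completed after the ACT review and session in the ACT group and without either in the non-ACT group

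*Protocol*

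**What the plan says.** Protocol section 6.4.2 names two measures that help to characterise the sample: "Baseline spirometry and PCD-QOL will be performed at the study visit for to assist with defining the study population". Spirometry is given a reason for its position: "As spirometry may cause inadvertent airway clearance it will be performed before the first MRI". No reason is given for the position of the questionnaire.

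The section then fixes a sequence for each group, introduced by "At the visit the following order of assessments will be used". In the ACT list, the step after the baseline scan is "5. Physiotherapy ACT review and ACT completion", which agrees with the narrative: "Participants in the ACT group will complete their usual ACT regimen immediately after the baseline MRI scan". QOL-PCD comes after the 1-hour MRI. In the non-ACT list it also comes after the 1-hour MRI, but no airway clearance precedes it on the schedule: "Those in the non-ACT group will be asked to not intentionally undertake any ACTs between the first and last MRI".

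On how the groups are formed, section 6.2.3 says: "We will allocate patient participants to groups to similarly distribute confounding factors including: age, gender and disease severity". On masking, section 7.5 says: "This is not a blinded study".

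**The concern.** A measure used to describe who was studied should be taken under the same conditions in everyone, and before the groups are handled differently. Here the ACT group has already had two things the non-ACT group has not. One is the airway clearance session. The other is a review that, under the airway clearance heading of section 6.4.2, is expected to ask participants how well they feel their regimen works for them. Such a conversation shortly before a self-completed health questionnaire could colour the answers, and participants know which group they are in.

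What is at stake is the description of the two groups. Allocation is not random and there are only 6 comparators, so a reader will look to the descriptive table for signs that the groups were alike. If the QOL-PCD scores differ, the table cannot show whether the difference existed on arrival or arose during the visit. If they agree, it cannot rule out that a prior difference was masked.

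**Working it through.** No arithmetic applies. The check is to set the two sequences in section 6.4.2 side by side and compare them with the stated purpose of the questionnaire.

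| Assessment | ACT group (n = 37), step of 8 | Non-ACT group (n = 6), step of 7 |
|---|---|---|
| Height and weight | 1 | 1 |
| Baseline spirometry | 2 | 2 |
| Oxygen saturation | 3 | 3 |
| Baseline MRI | 4 | 4 |
| ACT review and session | 5 | none |
| 1-hour MRI | 6 | 5 |
| QOL-PCD | 7 | 6 |
| 5-hour MRI | 8 | 7 |

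Reading down the table:

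1. The first four steps are identical in the two groups. Spirometry, the measure paired with QOL-PCD, falls among them.
2. The schedules part at step 5 of the ACT list. QOL-PCD falls after that point.
3. Before QOL-PCD, both groups have had two MRI sessions. The second scan is therefore not a difference between them. The only scheduled differences are the ACT review and the ACT session.
4. All 37 ACT participants, and none of the 6 non-ACT participants, answer after the review and session.

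The rest of the protocol was read for anything that would remove the difficulty:

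- It schedules no other QOL-PCD measurement, so there is no score from before the session.
- QOL-PCD is not among the quantitative outcomes listed in section 6.4.2, so the later slot is not explained by a wish to measure an effect of ACT. A single score after the session could not measure change in any case.
- QOL-PCD is not an eligibility criterion (section 6.2.1) and not among the allocation factors named in section 6.2.3. The primary outcome in section 6.2.2.1 is the VV% area under the curve from xenon MRI. None of these depends on when the questionnaire is completed.

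**The case against.** The strongest reply is that the protocol breaks no rule of its own. In the sentence quoted, the word baseline may belong to spirometry alone. The lists support that reading, since they label spirometry as baseline and leave QOL-PCD unlabelled. The only timing stated for the questionnaire is the study visit, and the schedule respects it. This stands: a reader might infer that the protocol contradicts itself by promising a baseline score and collecting a later one, but the text does not support that. The point rests on the descriptive purpose, not on the label.

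A reader might also infer that the score will be used as a covariate, a severity marker or formal evidence of comparability, and so object to conditioning on a post-treatment value. The protocol plans none of these uses. Section 6.2.3 takes severity from exacerbations needing antibiotics in the previous 12 months, and section 6.5 describes no model containing QOL-PCD.

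Nor is contamination of 37 scores shown. Participants have been on an ACT regimen for at least 3 months (section 6.2.1) and carry out their usual routine at the visit, so the session is not a new exposure. Whether one session or one conversation could move the score depends on the items and the recall period, which the protocol does not give. A long recall period would leave little room for distortion.

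Finally, the wait between the second and third scans is a convenient time for a questionnaire, and an earlier slot lengthens the period before the first scan for children as young as 5. That is a fair practical consideration, although the protocol does not offer it as the reason.

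What remains is that the descriptor is collected under unequal conditions, without a stated reason, and that no later analysis can recover a score from before the session.

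**Conclusion.** The point holds as a small design weakness. A self-reported measure meant to help define the study population is taken after the ACT review and session in 37 participants and without either in 6. The groups are open and not randomised. A difference between them in QOL-PCD could not be separated from a possible effect of the session or review.

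The size cannot be derived from the protocol and may be small. The primary VV% comparison, eligibility and the named allocation factors are unaffected. The conclusion assumes that the listed order is followed as written and that no unscheduled earlier score is collected.

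**What to change.** In both lists in section 6.4.2, move QOL-PCD to before the baseline MRI, for example next to height and weight. If that is impractical, place it after the baseline MRI but before the ACT review and session, and at the matching point in the non-ACT list. Either option gives a descriptor taken under the same conditions in both groups.

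The cost is one line moved in each list, a few more minutes before the first scan (under the first option), and one activity fewer in the wait between the second and third scans.

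If the later slot is kept, state the reason in section 6.4.2, report the score as collected after ACT in the ACT group, and do not present it as a pre-intervention characteristic.

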6.4.3. Phase 3, CTA Experiment-like task

The process of clinicians observing a videoed ACT regimen review with the phased introduction of information from functional imaging is a familiar task with manipulated variables or an experiment-like task³². The stimulus, which more typically is a questionnaire will be structured with three stages of information introduction:

- 1. Video of ACT review and ACT completion
- 2. ¹H MR images
- 3. ¹²⁹Xe MR images.

The clinician will be asked to share their clinical decision-making using Think-Aloud Problem Solving (TAPS) during the session. The clinician participant will be invited to pause the video at any point and there will be a series of defined junctures after each new information introduction where the clinician will be invited to describe the clinical decision making that has been triggered. If sufficient time lapses without any comments whilst watching the video, standard prompts to keep talking will be given.

The interviews are anticipated to be all conducted as a 1:1. However for the 2 reviews per centre which are opened up to the wider MDT, clinician preference and convenience will be prioritised and as such these may potentially be conducted as an MDT group at the local centre. These interviews can be conducted either face to face or via Microsoft Teams dependent of participant preference and Covid-19 restrictions. Audio recordings and observational notes of all the reviews will be taken. Each clinician will observe only the reviews of patients under their care.

6.5. Data Analysis

Quantitative:

Primary outcome metrics will be derived from ¹²⁹Xe MR ventilation images which will be analysed using protocols developed locally to quantify the 3D images. Lung ventilated volume percentage (VV%) will be calculated by manual segmentation of the ¹²⁹Xe images using in-house tested and validated methods⁴⁰. To measure ventilation heterogeneity, maps of coefficient of variation will be calculated as standard deviation/mean for an in-plane kernel of 3 x 3 pixels. Similar analysis will be applied to generate the ¹H MRI outcome measures from the surrogate maps of ventilation and perfusion derived from the ¹H PREFUL technique³⁹.

Correlation and agreement between the measures of ventilated volume at all three time points separately will be assessed using Spearman's rank-based correlation, and Bland-Altman plots of the difference in outcome versus the average analysis respectively. The inspiratory and expiratory ¹H anatomical images will be assessed for mucus and air trapping by a paediatric radiologist ([name]) as a surrogate for structural CT

Qualitative:

Data for the concept maps will be managed using CmapTools³². Recordings from the clinical reviews will be transcribed and the qualitative data will be managed using NVivo software. A member of the PPI group will be invited to be involved in verification of the analysis. Transcripts will be coded and thematic analysis will be used to analyse the data. Analysis will be overseen by [name] following the four-step Cognitive Task Analysis method³².

- 1. Preparation: data is prepared, data records, review project issues and questions, plan first data sweep.
- 2. Structure data: data immersion and decomposition using coding, cataloguing, frequency counts and descriptive statistics.
- 3. Discover meaning: identify central issues and emergent threads of meaning using contrast and comparison of accounts, describing cues, questions, and emergent threads.

4. Identify/represent key findings: communicating findings through incident accounts, timelines, and concept maps.

A concept map will be produced to represent and convey the clinical cues that physiotherapists consider when personalising and reviewing an ACT regimen. This is anticipated to include baseline spirometry, auscultation, quality of life, exacerbation frequency and patient/parental perspectives, for example, "ease of sputum clearance".

Integrated analysis:

6.6. Any iterative changes to the programme theory occurring during this prospective development study will be reflectively mapped²², for example change to an ACTs regimen due to learning from earlier participants. A map of the crosswalking⁴² between the units of analysis will be developed with data integrated using joint display tables^{43,44} and a case-by-case structured final report.

7. Safety assessments and Reporting

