Firstly, this research will provide insight into the critical decision-making of clinicians who review and individualise patients ACT regimens. We will capture how experts use clinical cues, providing transparency to complex clinical decision-making, turning tacit knowledge into explicit knowledge.

Secondly, this research will provide accurate measurements of the short-term effects of personalised ACT regimens by sensitive structural and functional regional assessment of the two patho-physiological processes which they target; ventilation and mucus plugging¹⁰. We will also measure the same-day natural variation of lung function in PCD without an ACT intervention. This is a first in PCD and will provide repeatability data for this project and future research and will aid understanding of the potential reversibility of abnormalities seen in chronic suppurative lung diseases. To do this, functional HP MRI, a radiation-free, non-aerosol generating, well tolerated, functional, sensitive, and specific tool^{11,12,13,14}, will be used as a surrogate for gold standard HRCT. I will use two types of MRI, highly sensitive HP MRI will serve as the primary outcome measure and secondly, we will evaluate a free-breathing ¹H MRI method that is potentially a more widely available tool as a surrogate to measure lung ventilation. Parental input and opinion from my PPI work has specifically expressed support for using MRI as a radiation free outcome measure within research.

Finally, we will explore if providing clinicians with the findings of the MRIs changes their ACT regimen recommendations to patients. This project is highly relevant to other Chronic Suppurative Lung Conditions including CF. As ACTs are preventative self-management measures it aligns with the NHS 10-year plan.

4. Review of existing evidence

ACTs are very commonly advised to people with PCD¹⁵, but a recent systematic literature search¹⁶ identified only one published study pertaining to ACTs in PCD. Although a statistically significant improvement in lung function was demonstrated with two different ACTs¹⁷ further evidence is needed.

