5.2. Aims

Quantitative research:

- 1. To measure lung health before and after airway clearance (compared to no intervention) in children and young people with PCD.
- 2. To compare the findings of two outcome metrics of lung ventilation pre and post airway clearance in children and young people with PCD.

Mixed methods research:

- 1. To explore how clinicians' make decisions when reviewing and personalising ACT regimens for children and young people with PCD.
- 2. To investigate how clinical decision-making changes with the introduction of functional imaging of the lungs.

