5.3. Objectives

Quantitative:

- To conduct a controlled before and after study to assess the short-term effects of an individualised airway clearance regimen on regional lung function versus no intervention over 4-hours using HP ventilation MRI and ¹H MRI in children and young people with PCD.
- 2. To assess the correlation and agreement between HP MRI and ¹H MRI pre and post ACT.

Mixed methods:

- 1. To undertake a knowledge elicitation exercise with physiotherapists using the critical decision method to produce a concept map to show how ACT regimens are personalised and assessed.
- 2. To carry out an experiment-like task using think aloud method to understand the clinical decision-making of clinicians when assessing the effects of personalised ACT regimens at three stages:
 - a) Watching a video-taped consultation of an ACT regimen review which provides data from existing clinical measures and tools.
 - b) With the introduction of proton MR images.
 - c) With the introduction of Ventilation MR images.

6. Plan of investigation

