- A research video summary to raise the public profile of the study and engage audiences for future research.
- Articles and presentations through social media platforms, newsletters, and family days.
- Age-appropriate output guided by PPI work, for example, a participant blog.

11. Strategy for taking the work forward if the research project is productive

This research will be the first phase of a larger package aiming to optimise the effects of ACTs and maintain long-term lung health. It will provide novel insight; for the first time, accurate measurements of the short-term effects of ACTs and an understanding of how this information would influence clinical practice. Subsequent steps will be based on the outcomes of this project and may involve:

- Assessing the longer-term effects of ACTs with both regionally specific and sensitive imaging and key clinical outcomes including Quality of Life, exacerbation rates, and hospital admissions.
- Comparison of imaging guided ACT regimen with standard ACT regimens.
- Comparison of the short-term effects of a single ACT versus an exercise session on regional ventilation and mucus clearance.

This work will have clinical potential in PCD and other Chronic Suppurative Lung Conditions, such as Cystic Fibrosis in which ACTs are commonly used.

HP MRI is a specialist tool, and phase 2 will enable understanding of the comparative role of surrogate methods for estimating lung ventilation from standard ¹H MRI. With new knowledge, any future clinical recommendations beyond this fellowship will require appreciate of costs, training requirements and availability of resources. In longer-term research beyond this project will involve health economists to assess the financial impact of any clinical recommendations.

Beyond this fellowship, this will be developed into a toolkit to guide less experienced clinicians and potentially patients through ACT personalisation Clinicians and patients will be consulted as stakeholders to find optimal dissemination pathways and to measure the impact of this educational material. Funding for this will be applied for towards the end of the fellowship.

12. Intellectual Property arrangements

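### Xenon and proton MRI are compared only visit by visit, so the plan meets objective 2 as worded but never tests whether proton MRI follows a patient's own change after airway clearance

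*Protocol*

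**What the plan says.** Section 6.5 (Data Analysis, Quantitative) sets out the comparison of the two modalities: "Correlation and agreement between the measures of ventilated volume at all three time points separately will be assessed using" the methods then named, "Spearman's rank-based correlation, and Bland-Altman plots of the difference in outcome versus the average analysis respectively". The three time points are baseline, 1 h and 5 h (section 6.4.2). Nowhere does the protocol plan a correlation or agreement analysis of the change from baseline, or of the area under the response curve, between the two modalities.

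The related statements of purpose are:

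- Objective 2 (section 5.3): "To assess the correlation and agreement between HP MRI and ¹H MRI pre and post ACT".
- Aim 2 (section 5.2): "To compare the findings of two outcome metrics of lung ventilation pre and post airway clearance in children and young people with PCD".
- Objective 1 (section 5.3) uses both modalities for the treatment effect, that is, the effect of an "individualised airway clearance regimen on regional lung function versus no intervention over 4-hours using HP ventilation MRI and ¹H MRI in children".
- The Rationale (section 3) describes a "free-breathing ¹H MRI method that is potentially a more widely available tool as a surrogate to measure lung ventilation".
- Section 11 expects that "phase 2 will enable understanding of the comparative role of surrogate methods for estimating lung ventilation from standard ¹H MRI".

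Section 6.1 describes a before-and-after design. Section 6.2.2.1 defines the primary outcome as change in xenon VV%, summarised as the area under the curve to 5 h.

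**The concern.** A correlation taken at a single visit asks whether patients with poorly ventilated lungs on xenon also look poorly ventilated on proton MRI. In a group aged 5 to 18 with varying disease severity, most of that correlation can come from stable differences between patients. Taking it at three visits in the same patients largely repeats one between-patient comparison. It does not address whether a patient whose xenon VV% rises after airway clearance also shows a rise on proton MRI.

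That second question matters for how the results will be used. The trial's treatment effect is a change, objective 1 lists proton MRI as one of the tools for it, and in phase 3 clinicians review regimens with proton images before they see xenon images. Three high correlations could be read as support for proton MRI as a stand-in for xenon MRI when judging airway clearance, although within-patient change was never compared.

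**Working it through.** The protocol gives no expected correlation, limits of agreement or variances for this comparison, so there is no stated figure to reproduce. Its one power statement concerns the primary xenon comparison and plays no part here. All variances below are assumptions.

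**1. Correlation at one visit when changes are unrelated.** Write xenon X = S + d and proton Y = S + e, where S is patient severity shared fully by both scans and d and e are independent short-term components of equal variance W. Then corr(X, Y) = Var(S) / (Var(S) + W), and the correlation of the changes is 0.

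| W as a share of Var(S) | Calculation | Pearson | Spearman, (6/π)·arcsin(r/2) |
|---|---|---|---|
| 5% | 1/1.05 | 0.95 | 0.95 |
| 10% | 1/1.10 | 0.91 | 0.90 |
| 20% | 1/1.20 | 0.83 | 0.82 |
| 100% | 1/2 | 0.50 | 0.48 |

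The Spearman column assumes bivariate normality. A persistent patient-by-modality error of variance M in each scan changes the formula to Var(S) / (Var(S) + M + W), so every figure falls.

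**2. What the Bland-Altman plots can show.** The bias at a later visit minus the bias at baseline equals mean xenon change minus mean proton change. A mean response missed by proton MRI therefore appears as a shift in bias. If the responses differ between scans within patients, the variance of the differences grows by the variance of (xenon response − proton response), so the limits widen.

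**3. Simulation of both statistics.** 4000 replicates, n=37, in VV% points. Assumed: between-patient SD 8, measurement SD 2 per scan, xenon response mean 3 and SD 3.

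| Proton response | Spearman, baseline | Spearman, after ACT | Spearman of change | Bias, baseline → after | SD of differences, baseline → after |
|---|---|---|---|---|---|
| A: none | 0.92 | 0.86 | 0.00 | 0 → 3.0 | 2.8 → 4.1 |
| B: same mean, unrelated to xenon | 0.92 | 0.80 | 0.00 | 0 → 0 | 2.8 → 5.1 |
| C: identical to xenon | 0.92 | 0.93 | 0.50 | 0 → 0 | 2.8 → 2.8 |

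The per-visit correlations lie between 0.80 and 0.93 in all three cases. The correlation of change separates C from A and B. The bias shift identifies A only. The wider SD flags A and B, but only if plots are set against each other across visits, and it cannot be told apart from noisier scans at the later visit.

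**4. Precision of a change correlation.** In C the response is fully shared, yet measurement error holds the correlation down: as Pearson, 3² / (3² + 2·2²) = 9/17 = 0.53, with 0.50 as the simulated mean Spearman. A Fisher-z 95% interval for 0.50 at n=37 is tanh(0.549 ± 1.96/√34) = tanh(0.549 ± 0.336), or 0.21 to 0.71.

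**The case against.** A reader might infer that objective 2 itself asks whether proton MRI detects the response to airway clearance, so that the analysis fails its own objective. The wording does not support this. Objective 2 asks for correlation and agreement before and after ACT, and analyses at baseline, 1 h and 5 h supply exactly that. Aim 2 can be read either as levels or as change. The Rationale and section 11 speak of estimating lung ventilation, not of response. Agreement on the level of ventilation is a legitimate question.

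A reader might also infer that the planned analyses can say nothing about response. That goes too far, because Bland-Altman plots are planned at every visit and step 2 shows that a missed mean response would move the bias.

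Two further points have force. The model in step 1 gives both scans identical patient severity, which breath-hold xenon and free-breathing proton imaging need not share, and the assumed ratios of 5% to 20% give the most striking figures. And objective 1 covers the group-level proton response, whose statistical model may properly be left to an SAP.

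What remains is narrower. Analysis at each time point separately is a stated choice, not an omitted detail. No comparison of plots across visits is planned. A group-level proton effect, or a shift in bias, would still not show whether the same patients respond on both scans.

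**Conclusion.** The point holds as a limited one. The plan meets the literal objective 2, but its per-visit correlations cannot distinguish a proton measure that follows a patient's response from one that does not, and its agreement plots bear on response only through a cross-visit comparison that is not planned.

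The range of 0.83 to 0.95 with unrelated changes rests on full sharing of severity and on assumed variance ratios. It shows what could happen and is not an estimate for this trial. The direction holds as long as the spread between patients exceeds the spread of within-patient change. The consequence is confined to a secondary objective and to any later claim that proton MRI can stand in for xenon MRI in judging airway clearance. The primary xenon comparison is unaffected.

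**What to change.** In section 6.5, keep the three per-time-point analyses as the answer to objective 2 and add alongside them:

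- Spearman correlation with a confidence interval, and a Bland-Altman analysis, of proton change against xenon change in ventilated volume, from baseline to 1 h and from baseline to 5 h.
- These for the ACT group and overall. Section 6.5 does not say whether the 6 non-ACT patients are pooled at 1 h and 5 h, when they are not post-ACT, so this should be stated. A pooled correlation of change can also reflect the difference between groups, so the ACT-group result should be shown separately.
- A sentence that proton MRI will not be described as a surrogate for response to airway clearance on the per-time-point results alone.

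No extra scans are needed, since both modalities are acquired at every session. The cost is a few sentences and a little more analysis. The change correlations will be lower than the per-visit ones and imprecise at n=37, because measurement error enters each change twice. The text should say this in advance so that a moderate value is not misread.
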